Based on preliminary data, we expect to observe larger age differences in DA D2-like receptor availability in the pallidum and frontal cortical regions, but smaller (but measurable) declines in the ventral striatum. We hypothesize that middle-aged adults will show significantly lower levels of DA release in the striatum and medial prefrontal cortex and DAT expression in the striatum compared to younger adults. Across both groups, we expect individuals with greater DA release in the ventral striatum and ventromedial prefrontal cortex to be more tolerant of effort costs.

Aim 2: To examine the influence of individual and age-related differences in DAT on dAMPH-induced DA release. Given that DAT is the primary site on which dAMPH acts, we will test the hypothesis that individual differences in DAT expression substantially predict DA release and the subjective effects of dAMPH. Because DAT declines with age, we additionally hypothesize that dAMPH-induced DA release will be lower in the middle aged than the young adult sample. We additionally predict that the combination of DA midbrain autoreceptor levels and striatal DAT levels will predict dAMPH induced DA release better than either index in isolation.

Aim 3: To examine the influence of dAMPH-induced DA release on cost-benefit decision making in young adulthood and late middle age.

We recently demonstrated that dAMPH increases tolerance of physical effort costs in healthy young adults. Young and middle-aged adults will complete a behavioral version of the effort-based task in two sessions (placebo, dAMPH). We expect that tolerance of physical effort will be increased under dAMPH in both age groups, with differences in the extent of modulation correlating with measures of baseline DA functioning and DA release.

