4.0 Study Procedures

4.1 Primary Study Procedures: The study involves 4 sessions: Informed Consent, Fallypride PET + placebo, Fallypride PET + oral d-amphetamine, and PE2I PET. The 3 PET sessions will be conducted within a 6 week window, and whenever possible within a 2 week time period.

4.2. Informed consent session: Informed consent will be obtained by [name] or approved study personnel after inclusion and exclusion criteria have been reviewed. This will be done in the Dept. of Psychology at Vanderbilt University. Written consent materials are provided to the participant originally when they complete the related IRB protocol #141812. Although given to participants during Part I of the study, Participants only sign the consent for the 2nd part of the study after completing the prior study and passing inclusion and exclusion criteria assessed during that study.

In the present study, participants are given time to read (or reread) the written informed consent document in a quiet private room. They are asked if they have any questions about the protocol. If they have no questions or the researcher has any concerns about whether they understand the procedures, the researcher will briefly review the steps of the study. Because the participants will have already completed IRB #141812, the researchers will already have some knowledge of the participants level of cognitive functioning, and if there is a concern about the participants ability to understand the procedures based on their past performance on cognitive measures they will be excluded from the study.

After the potential participant indicates they have read the document, [name] or his associate will briefly review specific procedures and their risks (especially those related to administration of amphetamine and PET radioisotopes), and the subject will be given a chance to ask questions. The participants will only be asked to sign the informed consent document after any and all questions have been answered.

After signing the informed consent, participants will receive a brief training on how to perform the two-stage task (this will help reduce the amount of time needed for training on that task on the fallypride PET scan days). Participants will also complete the Tests of Vigilance and Attention (TOVA: <http://www.tovatest.com/>), which assesses attention abilities and motor impulsivity.

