4.3 Specific procedures for female subjects of child-bearing potential: Premenopausal without hysterectomy or similar procedure, will need to have an additional blood draw within 48 hours prior to each PET session to rule out pregnancy (blood drawers will typically be scheduled within 36 hours preceding the planned time of radioisotope administration). Women who are premenopausal will be only studied within the first 10 days of their menstrual cycle.

4.4 Fallypride PET Sessions (with placebo or oral d-amphetamine).

Participants complete two [¹⁸F]fallypride PET sessions, each lasting approximately 7 hours. Scan sessions will all start in the afternoon. Subjects will be instructed to have a moderate lunch with no more than a single cup of coffee or tea before coming to the PET center. If the scan is not expected to start until after 5 PM, a light snack may also be eaten. After determination of blood pressure, respirations, pulse, temperature, an intravenous line will be placed in the forearm, the subject will complete ratings of their mood (using the and PANAS and the Amphetamine Interview Schedule administered on a laptop computer), and participants will have a brief neurological exam conducted by one of the study MDs. An initial blood sample for genotyping or estradiol levels (women only) will be acquired.

The subject will then receive a 0.43 mg/kg oral dose of d-amphetamine or placebo. The investigational pharmacy will prepare capsules with 10 mg, and 2.5 mg with dosing rounded to the nearest 2.5 mgs (for instance an individual weighing 80 kg would be rounded up to a 35 mg dose). The drug dose and placebo, will be placed by the pharmacist in identical containers, labeled with the subject's ID and scan day number. A sealed envelope indicating whether the dose is d-amphetamine or placebo will be included in case there is a need to break the blinding. The study physician, can quickly access this information if there is appearance of an adverse drug effect. Otherwise the study physician and experimenters who have contact with the participant will remain blind until the participant has completed their second PET scan. If a participant has an adverse event that necessitates any medication, or other intervention, the blind will be broken to the participant.

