7.0 Statistical Analysis Plan

Aim 1 tests the hypothesis that aspects of mesolimbic DA function are associated with age differences in decision behavior.

PET Analyses. A region of interest (ROI) approach will be used in the first set of analyses to examine age group differences in D2 binding (placebo BP_{ND}), DA release (Δ BP_{ND}), and DAT uptake in a set of eight brain areas. We will define subcortical (e.g., caudate, putamen, globus pallidus, thalamus) ROIs based on adapted methods developed for adults of various ages [173] by consultant [name]. We will define a lateral cortical ROI based on the results of a PCA (as in [153]) We will also anatomically define smaller key regions of interest in the midbrain (VTA/SN), ventral striatum (nucleus accumbens), and ventromedial prefrontal cortex using previously published guidelines [110,111] within individual subjects. For initial analyses all ROIs

will be averaged bilaterally, but follow-up tests will also be conducted to determine whether any ROIs warrant bilateral specification. D2 BP_{ND} (placebo) will be extracted for all eight ROIs, while DA release (Δ BP_{ND}) and DAT expression will be extracted from ROIs restricted to only those where there is substantial signal to noise (e.g., VTA/SN and striatal sites for DAT).

We will first test for expected age related differences in DA variables, using ANOVAs with Age group as the independent between subjects variable of interest. Separate analyses will be performed for BP_{ND}, Δ BP_{ND}, and DAT measures. We will also test for interactions between age group and region to test the hypothesis that there will be larger age differences in DA D2-like receptor availability in the pallidum and frontal cortical regions, but smaller (but measurable) declines in the ventral striatum. We expect that middle-aged adults will show significantly lower levels of DA release in the striatum and medial prefrontal cortex and DAT expression in the striatum compared to younger adults.

We will next test whether the dopaminergic measures predict behavioral differences in decision making. Across both groups, we expect individuals with greater DA release in the ventral striatum and ventromedial prefrontal cortex to be more tolerant of effort costs.

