Relative Influence of Different DA Measures. By assessing multiple aspects of the DA system it will be possible to assess the relative influence of different aspects of the DA system on behavioral measures. We will first use a PCA analysis of ROI data for cortical and subcortical ROIs for binding potential, striatal and ventromedial prefrontal DA release, and striatal and midbrain DAT. We expect there to be a positive correlation between all of these variables, reflecting an overall integrity of the DA system, but for separate components to arise reflecting region and measure specific variance [153]. We will then assess the relative impact of the DA variables, by utilizing step-wise regression to determine which variables provide the strongest influence on the behavioral variable, and whether, as predicted, a combination of DA measures provides significantly greater explanation of the behavioral variable than the measures taken in isolation. Further, we expect the inclusion of each additional measure of DA function to reduce the significance of the age effect on differences in sensitivity to effort costs. We expect that a model that includes D2 receptors, DA release, and DAT expression will reduce the age effect to

non-significance, indicating that the age effects are mediated by the DA variables. We will also formally test a mediation model.

Control for Morphometry: When imaging the aging brain it is extremely important to address age differences in morphometry. Aside from common issues that arise with BOLD fMRI [108], findings from prior PET studies of aging may be limited by a lack of control for morphometric changes with age. Lacking information on morphometry, it is possible that observed declines in striatal D2 BP_{ND} could be partially due to changes in grey matter rather than a specific D2 deficit. An additional *innovation* of this project is that we will examine the role of morphometric change, by directly examining whether controlling for grey matter volume changes the results, applying partial volume averaging corrections for ROI analyses, and voxelwise procedures based on voxelwise morphometry techniques (see [154,174] for method details and feasibility).

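### Baseline D2 and DA release share one placebo scan, so a positive D2-release correlation in the same region is not by itself evidence of DA-system integrity

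*Combined protocol and SAP*

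**What the plan says.** Three fallypride and DAT sessions are planned (section 4.1): "Fallypride PET + placebo, Fallypride PET + oral d-amphetamine, and PE2I PET". Section 4.4 confirms that there are two fallypride scans per person and no second drug-free one: "Participants complete two [¹⁸F]fallypride PET sessions, each lasting approximately 7 hours".

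Under PET Analyses in section 7.0 the measures are "D2 binding (placebo BP_{ND}), DA release (Δ BP_{ND}), and DAT uptake in a set of eight brain areas". The baseline measure covers every region: "D2 BP_{ND} (placebo) will be extracted for all eight ROIs". Whether ΔBP_ND is an absolute or a percent change is not stated.

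Under Relative Influence of Different DA Measures, the PCA takes "cortical and subcortical ROIs for binding potential, striatal and ventromedial prefrontal DA release, and striatal and midbrain DAT". The expected result is interpreted in advance: "We expect there to be a positive correlation between all of these variables, reflecting an overall integrity of the DA system". The same sentence also expects separate components for variance specific to a region or a measure. A step-wise regression and a mediation test follow.

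Aim 2 in section 2.0 adds a prediction that "the combination of DA midbrain autoreceptor levels and striatal DAT levels will predict dAMPH induced DA release better than either index in isolation". The Aim 2 paragraph in section 7.0 names only DAT as the explanatory measure.

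**The concern.** With one placebo scan per person, the number that serves as D2 is also the starting point of release. If that scan reads high because of reference-region noise, motion or calibration, the person appears to have both more receptors and more release. If it reads low, the person appears to have less of both. The error thus produces a positive correlation, which is also the sign the plan predicts and would credit to biology. An observed positive D2-release correlation, or joint loading on one component, cannot separate the two explanations.

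What is at stake is the integrity conclusion, in so far as it draws on D2 and release together, and to a lesser degree the prediction that midbrain autoreceptor level helps explain release. No section mentions the shared scan or test-retest error. The morphometry and partial-volume steps deal with grey matter, which is a different problem.

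**Working it through.** The plan states no figure for this correlation, so there is none to reproduce. The sizes below illustrate a mechanism that follows from the design.

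**Inputs from the documents.** One placebo and one drug fallypride scan (4.1, 4.4); D2 = placebo BP_ND and release = ΔBP_ND (7.0); 60 planned completers (3.2).

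**Assumed inputs (not in the documents).** In units of mean BP_ND: between-person SD σB = .10 to .20; scan-error SD σe = .03 to .10, equal and independent on the two days; true fractional release f with mean .07 and SD σf = .04, independent of true baseline B. Release is scored so that larger means more.

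**1. Same region, percent change.** With P = B + e1 and D = B(1 − f) + e2, the covariance of P with P − D contains +σe². For percent change,

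r ≈ σe² / √[(σB² + σe²)(σf² + 2σe²)].

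- CV 15%, error 5%: .0025 / √(.0250 × .0066) = .0025 / .01285 = .19.
- CV 20%, error 3%: .0009 / √(.0409 × .0034) = .0009 / .01179 = .08.
- CV 10%, error 10%: .0100 / √(.0200 × .0216) = .0100 / .02078 = .48.
- No scan error: 0.

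Simulation agrees: .08 to .48 over the range, .19 in the middle case, and 0.00 without scan error. At N = 60 the two-sided 5% threshold is |r| = .254. A simple pairwise test would be significantly positive in about 32% of null studies in the middle case, and in 10% to 97% over the range, against a nominal 2.5%.

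**2. Same region, absolute change.** Without any scan error,

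r = mσB / √[m²σB² + σf²(1 + σB²)], where m is mean release.

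At m = .07 and CV 15%: .0105 / √(.000110 + .001636) = .0105 / .0418 = .25. Over CV 10-20% this is .17 to .33. It arises because the same fraction of a larger baseline is a larger absolute amount. With scan error of 3-10% the total is .26 to .52.

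**3. Midbrain D2 against striatal release.** The numerator in step 1 is multiplied by ρ, the correlation of the two regions' errors within a scan (same CV and error assumed in both). At CV 15% and error 3-10%:

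| ρ | spurious r |
|---|---|
| 0 | 0 |
| .5 | .05 to .19 |
| .8 | .08 to .30 |

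If the true correlation were −.30, at CV 15%, error 5% and ρ = .8, the observed value would be about (−.30 × .15 × .04 + .8 × .0025) / .01285 = (−.0018 + .0020) / .01285 = .02. With ρ = 0 it would be −.0018 / .01285 = −.14, which is attenuation only.

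**4. Is the two-session mean a clean substitute?** Relate log(placebo/drug) to the mean of log BP_ND over both sessions (Oldham's method). The equal scan errors cancel, but the mean contains the drug-day value, which release itself lowers. In the same region,

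r ≈ −(σf²/2) / √[(σB² + σf²/4 + σe²/2)(σf² + 2σe²)].

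At CV 15% and error 5%: −.0008 / √(.02415 × .0066) = −.06. At error 3%: −.0008 / √(.02335 × .0034) = −.09, about as large as the +.10 it would replace. With scan error, CV 10-20% and release SD 4 to 6 points, simulation gives about −.03 to −.25. Across regions, this negative bias arises only in so far as release in the two regions moves together.

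**The case against.** The strongest reply is that the quoted sentence states an expectation about a descriptive PCA, not a test, and that the plan itself expects separate components by region and measure. That stands in part. No D2-release significance test is specified, so the rejection rates above show only how easily such a correlation would appear, and no effect on a particular loading has been shown. But the plan does say what a positive correlation would mean, and for this pair that meaning does not follow.

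A reader might infer more than the documents support:

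- *That the step-wise regression predicts release from D2.* Its outcome is the behavioral variable. D2 and release are both predictors.
- *That the SAP's Aim 2 model is compromised.* That paragraph names DAT, which comes from a separate scan. The autoreceptor prediction stands only in section 2.0. Reading it as placebo BP_ND in VTA/SN is an inference, though no other D2 measure is planned there. The artefact is zero if regional errors are independent.
- *That scan error explains the whole correlation under absolute change.* At the assumed values much of it is scaling with baseline (step 2).
- *That the two-session mean should replace placebo D2, or that release must leave the PCA.* The first exchanges a positive bias for a negative one, and the documents do not supply the values needed to say which is larger. The second gives up the joint assessment that the PCA is for, when a limit on interpretation is enough.

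**Conclusion.** The concern holds for D2 and release in the same region. The direction of the bias follows from the design, given some placebo-scan error and release scored so that larger means more. Its size cannot be fixed from the documents. Under the assumptions above it is about .08 to .48 for percent change, and .19 in the middle case. The upper part of that range overlaps the correlations of 0.3 to 0.6 that the Statistical Power paragraph cites from related studies. For midbrain autoreceptor level and striatal release the artefact is conditional on error shared across regions and may be nil. The D2-DAT and release-DAT correlations are untouched by the shared placebo scan. The point concerns interpretation: it does not affect the age-group comparisons of each measure and has not been shown to affect the behavioral results.

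**What to change.** In section 7.0, Relative Influence of Different DA Measures:

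1. Define DA release as a percent or log-ratio change from placebo, with the sign stated.
2. Base any conclusion about shared DA-system integrity only on pairs from separate scans: D2 with DAT, and release with DAT. The PCA may keep all measures, with a sentence saying that joint loading of D2 and release is not read as integrity.

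For the autoreceptor-release prediction in section 2.0, Aim 2:

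3. Alongside the placebo-only analysis, report as a sensitivity analysis the association of log(placebo/drug) with the two-session mean of log BP_ND. State that the two-session version is biased negatively and the placebo-only version positively, to extents that depend on steps 3 and 4 above, and draw a conclusion only if both agree.

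The cost is a narrower integrity claim, a few sentences of SAP text and one extra analysis of data already planned. No further scan or participant is needed.

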Aim 2 examines the hypothesis that individual and age-related differences in DAT are associated with dAMPH-induced DA release. This will be studied using striatal ROIs and ANOVA with age group serving as a between subjects variable.

Aim 3: To examine the influence of dAMPH-induced DA release on cost-benefit decision making in young adulthood and late middle age. We expect that tolerance of physical effort will be increased under dAMPH in both age groups, with differences in the extent of modulation correlating with measures of baseline DAT functioning and DA release. This will be accomplished by ANOVA analysis with age group as a between subjects variable.

Mediation Analyses: In each of the above cases we will utilize a mediation analysis to test whether expected age differences in behavior (effort performance, responsivity to d-AMPH) are mediated by age related differences in regional DA functions.

Exploratory voxel-wise analyses: Beyond the ROI analyses, more exploratory whole-brain voxelwise analyses will be conducted. For these analyses, individual difference measures (e.g., choice preferences, trait affect, cognitive ability, etc) and age will be mean-deviated and entered as regressors of interest to predict BP_{ND}. The resulting whole-brain maps will be thresholded at whole brain $p_{\text{cluster-corrected}} < 0.05$.

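### Step-wise selection and the test of the combination use the same data, and loss of significance of the age effect is read as mediation without a rule that the formal mediation test decides

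*Combined protocol and SAP*

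**What the plan says.** All of this is in section 7.0, mainly under Relative Influence of Different DA Measures.

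- **Step-wise regression.** After a principal component analysis of "cortical and subcortical ROIs for binding potential, striatal and ventromedial prefrontal DA release, and striatal and midbrain DAT", the plan assesses relative impact by "utilizing step-wise regression to determine which variables provide the strongest influence on the behavioral variable". The same sentence gives it a second task: whether "a combination of DA measures provides significantly greater explanation of the behavioral variable than the measures taken in isolation". No candidate list, entry or removal threshold, hold-out sample or selection-adjusted test is stated. It is not said whether ROI values or components enter.
- **Candidates.** Under PET Analyses, placebo D2 binding "will be extracted for all eight ROIs"; the number of release and DAT regions is left open. On correlation the plan says: "We expect there to be a positive correlation between all of these variables".
- **Reading of the age effect.** A model with D2 receptors, DA release and DAT is expected to bring the age effect to "non-significance, indicating that the age effects are mediated by the DA variables".
- **Formal test.** The next sentence is "We will also formally test a mediation model". The Mediation Analyses paragraph also plans mediation testing, with this stated purpose: "to test whether expected age differences in behavior (effort performance, responsivity to d-AMPH) are mediated by age related differences in regional DA functions". Neither place names the method or the indirect-effect measure, or says which result prevails if they disagree.

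**The concern.** Two claims in this subsection could be reached when they are false.

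The first is that several DA measures together beat any one of them. If the data choose which measures enter, an ordinary p-value for the added measures ignores that choice and overstates the evidence.

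The second is that DA explains the age difference in effort choice. Non-significance of age after adjustment does not show that anything passed through DA. The plan itself expects the DA measures to differ by age. Such variables are collinear with age group, so they widen the standard error of the age coefficient whether or not they affect behaviour. The artefact is worst when the behavioural age effect is only just detectable. Section 1.0 says that effort preference has not been studied in middle-aged or older adults, so the low end of the plan's effect range cannot be excluded.

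**Working it through.** **1. The plan's own figures (section 7.0, Statistical Power).**
- Group difference d=0.75, two-sided .05, power .80: the noncentral t-test gives 29 per group, 58 in total, against the plan's 60. Power at 30 per group is 0.815.
- Within-group r=.5 with two covariates: ((1.960+0.842)/atanh(.5))² + 3 + 2 = 31.01, rounded up to the plan's 32.
- N=64 with three covariates: power 0.987, consistent with the plan's statement of over .95.

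The sizing reproduces. It covers group differences and correlations, not step-wise selection or mediation.

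**2. False combination after step-wise selection.**

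Assumed, because the plan does not say: N=60, entry p<.05, removal p>.10, exactly one measure related to behaviour (r=0.5), and inter-measure correlation 0 to 0.6. The event counted is that two or more measures are retained.

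Candidate counts:
- 3: one value each for D2, release and DAT, or a component-reduced set.
- 6: one value for each of cortical D2, subcortical D2, striatal release, ventromedial prefrontal release, striatal DAT and midbrain DAT.
- 12: the eight D2 ROIs plus the last four.

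For uncorrelated candidates, K−1 irrelevant measures each have a 5% chance of entering, so the rate is about 1 − 0.95^(K−1):
- K=3: 1 − 0.95² = 9.8%
- K=6: 1 − 0.95⁵ = 22.6%
- K=12: 1 − 0.95¹¹ = 43.1%

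Simulation across correlations 0 to 0.6 gives about 7-10%, 15-23% and 28-44%; the lower figures belong to the higher correlations. Forcing age group into the model changes the rates by at most 2 points. If no measure matters, two or more are retained in about 1%, 3% and 8-11%.

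**3. Loss of significance when DA has no effect.**

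Inputs: 30 per group (plan); behavioural d from the plan's range of 0.75-1.5. Assumed: DA age difference d_M = 0.75-1.5, and within-group correlation ρ between the three DA measures of 0.5 to 0. The documents give neither.

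For two equal groups, the variance of the age coefficient is multiplied by VIF = 1 + D²/4, where D² = 3·d_M²/(1+2ρ). The expected t for age before adjustment is d·√15. The critical value is about 2.00.

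- d=0.75: t = 0.75 × 3.873 = 2.90.
- d_M=1.0, ρ=0.5: D²=1.5, VIF=1.375, standard error ×1.17, expected t = 2.48.
- d_M=1.5, ρ=0: D²=6.75, VIF=2.69, standard error ×1.64, expected t = 1.77, below the critical value.
- d=1.5 in that same worst case: 5.81/1.64 = 3.54, still clear.

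Simulated share of significant age effects that become non-significant (first figure ρ=0.5, second ρ=0):

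| Behavioural d | d_M=0.75 | d_M=1.0 | d_M=1.5 |
|---|---|---|---|
| 0.75 | 15-24% | 22-35% | 38-54% |
| 1.0 | 6-11% | 10-19% | 21-38% |
| 1.5 | under 1% | under 1% to 2% | 2-9% |

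These rates are conditional on a significant age effect at the start (81-82% of data sets at d=0.75). Over all data sets, d=0.75 with ρ=0.5 gives 13%, 18% and 30%. A smaller DA difference (d_M=0.4, ρ=0.5) gives 8%, 3% and 0% at behavioural d=0.75, 1.0 and 1.5.

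**4. The same null case with a formal test.** Also requiring a significant indirect effect cuts false mediation to about 2% or less. The indirect-effect test alone also holds its level: 3.9-4.9% for one composite mediator (joint-significance test), and 1-5% for the total indirect effect of five mediators (95% bootstrap interval).

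**The case against.** The strongest reply is that the mediation sentence is an expectation, not a decision rule. Formal mediation testing is planned in two places, so harm arises only if the investigators let lost significance overrule it. This stands in part. A reader might infer that the plan has no mediation test, or that lost significance alone decides; the documents support neither. But the sentence does state what non-significance would indicate, the formal test is only an addition, and nothing says which prevails.

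Second, the plan does not say that one step-wise run settles the combination claim, or that it is settled by counting retained variables. A nested R-squared comparison would fit the words equally well. That is correct: the event simulated above stands in for a test the plan leaves unspecified. A nested comparison on variables chosen by the same data would still carry the selection problem. The prior component analysis might reduce the candidates, but even three uncorrelated components give about 10%.

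Third, the sizes depend on inputs the plan does not give. This stands in full, and is why ranges are shown. The direction is not in doubt, but the size is.

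Finally, this is one subsection of a mechanistic study in healthy volunteers, and no safety or treatment claim depends on it. That limits the weight of the point but does not remove it.

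**Conclusion.** The concern holds as a defect of inference in this subsection. Selection and significance testing share the same data, and lost significance is given a meaning it does not have while the formal test has no stated precedence.

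The false-combination risk is modest with three candidates and substantial with six or twelve; the plan does not say which applies. The false-mediation risk is material at behavioural d=0.75-1.0 and small at d=1.5. Both sizes rest on the assumed thresholds, candidate counts, correlations and DA age differences. Confidence is high in the wording gap and lower in any single percentage.

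A reader might extend the point to the Aim 1 age-group ANOVAs; they involve neither selection nor this reading and are unaffected. The D2, release and DAT model used for the age effect names its three kinds of measure in advance, so selection bears mainly on the combination claim. The point is worth correcting before PET measures are related to behaviour.

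**What to change.** In section 7.0, Relative Influence of Different DA Measures:

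1. In "non-significance, indicating that the age effects are mediated by the DA variables", delete everything from the word indicating onward. State that mediation is claimed only if the formal test of the indirect effect excludes zero (for example, a 95% bootstrap interval for the total indirect effect of the D2, release and DAT model), and that this governs over any change in the p-value of age.
2. Label the step-wise results exploratory and draw no significance claim from them.
3. Take any claim that a combination is significantly better from a nested-model comparison using the plan's own D2, release and DAT model, with its variables fixed before PET measures are related to behaviour.

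The cost is SAP wording: no new data or procedures. Step-wise findings become descriptive, and power at N=60 is moderate. As a guide from larger sets than the three-measure model:
- A four-measure comparison that must reject every one-measure model has 60-73% power if two measures each have a standardised coefficient of 0.4 (assumed), and 10-28% at 0.3.
- The total indirect effect of five measures has 31-63% power if one measure alone mediates (coefficient 0.4), and 84-99% if all five share the effect (0.15 each).

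Adjusting intervals for the number of regional mediators in the Mediation Analyses paragraph, or collapsing the eight D2 regions into one component within a five-measure set, are optional design choices with their own drawbacks. Neither is needed to correct this point.
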